Team Member Epidemiology:					
Project Team:					
Study data source:		UnitedHealth 2009 through 2015 MarketScan 2009 through 2015			
Objectives:		The objective of this study is to provide a description of patients with non-valvular atrial fibrillation at risk for stroke initiating oral anticoagulants and a description of existing utilization patterns for warfarin and for the new oral anticoagulant (NOAC) medications as they become available over time.			
Methodology/Study design:		Observational cohort study			
Expected number of patients:		~ 200,000 (estimated size of the unmatched cohort including warfarin, dabigatran, and other NOACs)			

Main criteria for inclusion:	A recorded diagnosis of atrial fibrillation. Initiation of oral anticoagulant medication. At least 18 years of age on the date of anticoagulant initiation CHA ₂ DS ₂ -VASc score ≥ 1
-------------------------------------	--

Name of company:		
Boehringer Ingelheim GmbH		
Name of product: PRADAXA®		
Name of active ingredient: dabigatran		
Protocol date 31 July 2014	Study number 1160.177	Planned study period Jun 2012 – Jun 2017
Main criteria for exclusion:	Patients with less than 12 months enrolment in the UnitedHealth Research Database or MarketScan database preceding the date of first dispensing will be excluded. Also excluded will be patients with missing or ambiguous age or sex information. Patients with documented evidence of valvular disease. Patients with prior use of any oral anticoagulant	
Study product:	PRADAXA (dabigatran)	
Comparison group:	Warfarin, and other new oral anticoagulants as they become available	
Expected duration of exposure:	Until treatment discontinuation as observed in the data source; the study objective is to describe observed utilization	
Outcomes:	
This study will describe the patient population with non-valvular atrial fibrillation initiating oral anticoagulants and anticoagulants utilization patterns. Utilization measures include:
 
 • Number/proportion of patients initiated on specific anticoagulants and anticoagulant doses • Time until treatment discontinuation (gap > 30 days) • Time until treatment switch 	

**Data Analysis
Methods:**

Analyses are inherently descriptive in nature. Utilization patterns will be examined overall

The initial analyses will be based on currently available data from Jan 2009 – Jun 2012. Subsequent analyses will include additional data in 6-month increments (Jul 2012 – Dec 2015).

PROTOCOL CHANGES

Informed by the first two analyses (Interim Report 1 and 2), the analyses were streamlined to remove redundant information and focus on the main outcomes of interest. The specific changes are documented in the table below.

Date	Versi on	Type of Change	Comments
31 July 2014	V 2.0	Addition of MarketScan data throughout the document	Added to increase the population size (Synopsis, Study design, Data Sources 3.1)
31 July 2014	V 2.0	Treatment gap to define end of follow-up changed from 6 months to 30 days	Many patients will be censored for administrative reasons before they reach a 6-month treatment gap, reducing the opportunity to observe between-treatment differences. Treatment discontinuation will therefore be evaluated using a 30 day treatment gap instead in the main analysis,
31 July 2014	V 2.0	Prevalence of use was changed to treatment initiation rates	Change implemented to streamline the analyses and focus on the main outcomes of interest (Main analyses 3.6.1)
31 July 2014	V 2.0		
31 July 2014	V 2.0	Persistence over time is considered a secondary outcome	Informed by the first analyses, persistence over time is considered of high importance to describe anticoagulant utilization (Outcomes 3.4 and Main analyses 3.6.1)
31 July 2014	V 2.0	12-month covariate	The covariate assessment period was changed from 6 months to one year for

		assessment period	consistency with the comparative safety protocol (Covariates 3.5)
31 July 2014	V 2.0	Utilization measures are examined in a propensity-matched cohort	To ensure a valid comparison of utilization measures, these measures are examined in a propensity-score matched cohort, rather than in the overall study population (Main analyses 3.6.1)
31 July 2014	V 2.0		
31 July 2014	V 2.0		

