3.2 STUDY POPULATION

From the UnitedHealth Research Database and MarketScan source data, we will identify patients with a recorded diagnosis of non-valvular atrial fibrillation at risk for stroke who initiated anticoagulant medications between January 2009 and June 2012. Additional increments of data will be added as they become available (in 6 month intervals). Data from the time period before dabigatran was launched will be used to describe the characteristics of warfarin patients before the availability of NOAC, and to evaluate a potential shift in characteristics of warfarin patient over time as NOAC enter the market.

Inclusion criteria²:

- Any person within the source data who had a diagnosis of atrial fibrillation recorded (ICD-9 Dx code of 427.31, atrial fibrillation) and received a dispensing of an anticoagulant medication (warfarin and dabigatran for the initial analysis; with others to be added as they become available for stroke prevention in later time intervals) in the timeframe of the study.
- The first dispensing is preceded by at least 12 months continuous enrollment in the study database, defined as <32 days enrollment gap using enrollment and disenrollment dates. The study will thus focus on 'new initiators' defined operationally as no dispensing of any anticoagulant in the prior 12 months. Note that new initiators will turn into prevalent users over time.
- Patients' follow-up will end when there is a treatment gap of ≥ 30 days. If the same patient re-initiates treatment later on – after a treatment gap of ≥ 12 months –, (s)he may re-enter the cohort at that time (an indicator variable will be created to identify such patients, known as former users).
- 18 years or older at the time of treatment initiation
- CHA₂DS₂-VASc score³ ≥ 1

Exclusion criteria:

- patients with less than 12 months continuous enrollment in the study database without anticoagulant use before the first dispensing of anticoagulant medication.
- Patients with missing or ambiguous age or sex information.
- Patients with documented evidence of valvular disease defined as at least 1 inpatient or outpatient ICD-9 Dx code of [R11-4334]
 - 394.x (diseases of mitral valve)
 - 395.x (diseases of aortic valve)
 - 396.x (diseases of mitral and aortic valve)
 - 397.x (diseases of other endocardial structures)
 - 398.9x (other and unspecified rheumatic heart diseases)
 - V42.2 (heart valve replaced by transplant)

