3.6.1 Main analyses

Analyses in this protocol are inherently descriptive in nature. The analyses described below will initially be conducted for the base cohort (Jan 2009- June 2012 data). Analyses will be updated at 6-month intervals as more data become available for the existing cohort(s) and new users are identified within the additional time period (July 2012- Dec 2015 data). As new data become available, we will characterize the patients newly initiated on treatment during that time period separately, in order to enable characterization of the shift in patient characteristics and use over time. In addition, short and long-term outcomes for the already existing cohorts (i.e., patients identified in previous time periods) will be updated with the newly available information in terms of switches, discontinuations, adherence and persistence.

A 12-month time window of no treatment is used to define a “new” treatment episode (i.e., incident user). Patients who re-initiate treatment after a treatment gap of \geq 12 months will re-enter the cohort as former users.

Primary outcomes:

Treatment initiation over time:

The yearly anticoagulation initiation rate will be estimated as the proportion of patients who initiated treatment among the source cohort of patients with non-valvular atrial fibrillation who met the study inclusion criteria and were not already on treatment. To identify the

source cohort of treatment candidates in a given calendar time window (i.e., the denominator for the rate), all patients with at least one day eligibility will be identified. A random date within the first eligibility period (if more than one) within the calendar time window will be selected and set as the index date. The cohort inclusion and exclusion criteria will be evaluated using this index date. Patients who were dispensed an anticoagulant before the assigned index date (prevalent users) will be removed from the denominator, unless they are identified as new initiators (i.e., included in the numerator) for that particular time period.

Characteristics of anticoagulant users:

The analyses will describe the proportion of patients treated with various oral anticoagulants, as well as the characteristics of these patients. For the NOACs, the starting dose will also be considered. Analyses will be conducted

as well for the combined cohort of incident and former users. Characteristics for the combined cohort will be presented in the core set of tables;

—
—
—

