11. APPENDICES

11.1 APPENDIX 1: LIST OF FIGURES AND TABLES

List of Core Tables

These tables will be generated separately for United and MarketScan; and will be presented only for incident and former users combined, unless meaningful differences between characteristics of incident and former users are observed.

- | | |
|----------|--|
| Table 1 | Treatment initiation over time |
| Table 2 | Characteristics of Anticoagulation Users: all time periods combined |
| Table 3 | Characteristics of Anticoagulation users: latest time period |
| Table 4 | Adherence metrics for Anticoagulation users: all time periods combined |
| Table 5 | Adherence metrics for Anticoagulation users: latest time period |
| Table 6 | |
| Table 7 | Characteristics of continuers, switchers (combined and by treatment switched to), and discontinuers at 3 months : characteristics measured during the 12-months preceding treatment initiation . |
| Table 8 | Characteristics of continuers, switchers, and discontinuers at 3 months: characteristics measured during the 3-months immediately preceding the event (day of switch, day of discontinuation, day 90 for continuers). |
| Table 9 | Characteristics of continuers, switchers, and discontinuers at 6 months : characteristics measured during the 12-months preceding treatment initiation . |
| Table 10 | Characteristics of continuers, switchers, and discontinuers at 6 months: characteristics measured during the 3-months immediately preceding the event (day of switch, day of discontinuation, day 180 for continuers). |
| Table 11 | Characteristics of continuers, switchers, and discontinuers at 12 months : characteristics measured during the 12-months preceding treatment initiation . |
| Table 12 | Characteristics of continuers, switchers, and discontinuers at 12 months: characteristics measured during the 3-months immediately preceding the event (day of switch, day of discontinuation, day 360 for continuers). |

List of Core Figures

[figure not shown]
These figures will be generated separately for United and MarketScan

- Figure 1: Cumulative incidence of treatment switches - 30 day gap

Figure 2: Cumulative incidence of treatment discontinuation – 30 day gap

Figure 3: Cumulative incidence of treatment switches or discontinuation – 30 day gap

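### The synopsis excludes any prior oral anticoagulant use, but sections 3.2 and 3.6.1 re-admit former users, and Appendix 1 by default pools them with incident users in the core tables, including the adherence tables

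*Combined protocol and SAP*

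**What the plan says.** **Who is eligible.** The synopsis, under main criteria for exclusion, lists "Patients with prior use of any oral anticoagulant" and states no look-back window. Section 3.2 has no such exclusion. Its new initiators are "defined operationally as no dispensing of any anticoagulant in the prior 12 months", and the corresponding exclusion removes only "patients with less than 12 months continuous enrollment in the study database without anticoagulant use before the first dispensing of anticoagulant medication".

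**Who comes back.** Section 3.2 says that "follow-up will end when there is a treatment gap of ≥ 30 days". If the patient restarts after a gap of at least 12 months, "s)he may re-enter the cohort at that time (an indicator variable will be created to identify such patients, known as former users". Section 3.2 words this as a possibility, section 3.6.1 as a certainty: "12 months will re-enter the cohort as former users".

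**What is shown.** Section 3.6.1 places the characteristics of the combined cohort in the core tables. Appendix 1 says that the core tables "will be presented only for incident and former users combined, unless meaningful differences between characteristics of incident and former users are observed". That list includes Tables 4 and 5, the adherence metrics. For Core Figures 1–3 (cumulative incidence of switching, discontinuation, or either), Appendix 1 says only that they are produced separately by database.

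**How arms are made comparable.** Section 3.6.1 matches NOAC to warfarin patients 1:1 on a propensity score (caliper 0.05) within calendar quarter. The visible text does not name the former-user indicator as a matching variable, and the covariate list is redacted.

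**The concern.** A reader of the synopsis expects a cohort with no earlier anticoagulant use. The body builds a cohort of incident users plus restarters, and its default tables do not separate the two.

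The restarters are selected on something close to the outcome. Each has had a gap of at least 12 months and so has already met the Table 3 definition of discontinuation (at least 30 days). Section 3.6.1 defines non-persistence, the secondary outcome, as discontinuation or switch. If people who stopped once are more, or less, likely to stop again, the pooled figure describes neither group well.

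The earlier treatment also lies outside the 12-month covariate period given in the Protocol Changes table, because the gap is at least as long as that period. Covariates built from dispensings in that window cannot carry it; only the indicator can. If former users make up different fractions of the matched warfarin and NOAC arms, the arms can differ in persistence for a reason that is not the drug. Section 3.6.1 notes that dabigatran was launched in October 2010, so episodes that ended earlier were not on a NOAC. It is a reasonable inference, though not a documented fact, that former warfarin users do not choose at random when they restart.

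**Working it through.** **Step 1: compare the rules for one patient.** Take a patient who is dispensed warfarin, stops, has 12 or more months without anticoagulant, and restarts.

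- Synopsis: excluded at restart, because there was prior use.
- Section 3.2: the restart qualifies, and the patient may re-enter with a flag.
- Section 3.6.1: the patient re-enters as a former user.
- Appendix 1: by default the patient is counted in Tables 4 and 5 together with incident users.

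The synopsis and the body therefore give opposite answers for the same patient.

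**Step 2: inputs for size.** The documents give neither the share of former users nor their difference in persistence from incident users. Assumed ranges are a share of 1% to 20% and a gap of 5 to 20 percentage points. The plan has no figure of its own on this point to reproduce. Its Table 1 serves only as a check on the precision formula, s.e. = √(p(1−p)/n): √(0.10 × 0.90 / 10,000) = 0.3%, as printed, and the other seven rows also reproduce.

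**Step 3: shift in a pooled estimate** = share × gap, in percentage points.

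| Former-user share | Gap 5 | Gap 10 | Gap 20 |
|---|---|---|---|
| 1% | 0.05 | 0.1 | 0.2 |
| 5% | 0.25 | 0.5 | 1.0 |
| 10% | 0.5 | 1.0 | 2.0 |
| 20% | 1.0 | 2.0 | 4.0 |

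**Step 4: shift in a between-arm contrast** = difference in share × gap, with no true drug difference.

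| Shares in the two arms | Gap 5 | Gap 10 | Gap 20 |
|---|---|---|---|
| 5% vs 2% | 0.15 | 0.3 | 0.6 |
| 10% vs 5% | 0.25 | 0.5 | 1.0 |
| 15% vs 5% | 0.5 | 1.0 | 2.0 |

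**Step 5: compare with sampling error.** The yardstick for a contrast is the s.e. of a difference, not the single-proportion errors in Table 1. Assume 60% persistence, treat the arms as independent and ignore censoring: s.e. = √(2 × 0.60 × 0.40 / n per arm).

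- 10,000 per arm: √(0.48 / 10,000) = 0.69 points.
- 50,000 per arm, the most that 1:1 matching could yield from a total of 100,000 in a database: √(0.48 / 50,000) = 0.31 points.

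The Step 4 shifts of 0.15 to 2.0 points lie on both sides of these values, so the assumed ranges do not settle whether the shift exceeds sampling error.

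**The case against.** The best case for the plan is that the synopsis line is shorthand. Sections 3.2, 3.3 and 3.6.1 and the notes to Table 3 all use the 12-month washout. Re-entry is deliberate and flagged, and including restarters suits a study of existing use. Section 4 already concedes that new initiators may have been treated before enrolment, so never-users cannot be isolated completely. The analyses are descriptive, and section 8 says that the tables will not make explicit comparisons.

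Much of this stands. It makes the conflict one of wording, but the wording still has to be reconciled. Section 4 covers only unseen use before enrolment, not restarters whom the database itself identifies. The descriptive label does not remove the comparison either: section 3.6.1 gives valid comparison of utilization as the reason for matching.

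A reader might also infer several stronger things that the documents do not support:

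- *That incident-only persistence will not be reported.* Text is missing in section 3.6.1 just before the combined cohort is mentioned, and the surviving words suggest that another cohort is analysed too.
- *That only baseline differences can trigger a split.* Appendix 1 says characteristics without qualification, and section 8 counts adherence among follow-up characteristics. The trigger is unclear, not demonstrably limited to baseline.
- *That former-user status is left out of the propensity score.* The covariate list is redacted, so this cannot be judged.
- *That the core figures pool the two groups.* Appendix 1 states the pooling rule for tables only.
- *That the bias exceeds sampling error.* Step 5 shows that this depends on the assumptions.

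Large former-user shares also lack documentary support. To be recognised as a former user, a patient needs 12 months of enrolment, a treatment episode and then at least 12 months off treatment, so more than two years in all. Section 4 puts the average history at about two years.

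**Conclusion.** The point holds as a reconciliation and reporting issue. The synopsis and the body define different cohorts. The default core tables, including adherence Tables 4 and 5, mix incident users with patients who have already discontinued once, and the condition for separating them has no threshold and does not clearly cover persistence.

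The effect on results is possible but not demonstrated. Under the assumed ranges, a pooled persistence estimate moves by 0.05 to 4 points, and a matched contrast by 0.15 to 2.0 points if the former-user shares differ by 3 to 10 points. Both ranges rest on assumed shares and gaps; with few former users or similar persistence the effect is negligible. The change is still worth making, because the flag is already planned and the subgroup is tied by definition to the secondary outcome.

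**What to change.** 1. Align the synopsis exclusion with section 3.2 by stating the 12-month window and the re-entry of former users, and use the same wording on re-entry in sections 3.2 and 3.6.1.
2. Show Core Tables 4 and 5 for incident users and for former users separately, whether or not their characteristics differ.
3. State which population Core Figures 1–3 use, and show incident users there.
4. Match exactly on the existing former-user indicator as well as calendar quarter. Including it in the propensity score, if that is already planned, would not guarantee balance on it.
5. If the conditional split is kept for the other core tables, define what counts as a meaningful difference and which characteristics it covers.

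The cost is protocol wording, one more exact-match variable and extra table rows. No new data are needed. The downside is that a few former users will go unmatched in sparse quarters.

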1. BACKGROUND¹

A number of new oral anticoagulants are being developed and marketed to replace vitamin K antagonists (e.g., warfarin), one of the most important drugs in modern medicine.[\[P12-08021\]](#) Unlike vitamin K antagonists, these new drugs do not require dose titration involving intensive therapeutic monitoring of prothrombin time to achieve target anticoagulation within a narrow therapeutic range. In Phase III studies, these drugs were found to be therapeutically advantageous or non-inferior over warfarin; however, little is known about their efficacy relative to one another.[\[R11-4190; P09-11669; R11-4223\]](#) In the coming years, as many as six new anticoagulants could be on the market and a lack of valid comparative evidence will hinder prescriber and payor decision-making.

To date, these drugs have been studied in pre-marketing clinical trials for three separate indications: (1) prevention of stroke and systemic embolism among patients with atrial fibrillation; (2) prevention of deep venous thromboembolism (DVT) among patients undergoing hip or knee replacement therapy; and (3) treatment of venous thromboembolism (VTE). Phase III clinical trials comparing dabigatran, rivaroxaban, and apixaban to warfarin in patients with non-valvular atrial fibrillation (NVAF) have been completed. [\[R11-4190; P09-11669; R11-4223\]](#)

It was hypothesized that the effectiveness and safety of oral anticoagulants in stroke prevention will strongly depend on their use patterns. [\[P12-08021\]](#) A thorough understanding of (1) the existing utilization patterns for warfarin, and changes in this utilization that occur after the introduction of NOACs; (2) differences in utilization patterns between warfarin and NOACs; and (3) differences between specific NOACs, will help with the design, analysis and interpretation of comparative effectiveness and safety studies for the NOAC.

This protocol is for a series of descriptive analyses starting with the cohort of patients with non-valvular atrial fibrillation identified in the currently available Jan 2009- Jun 2012 data, followed by inclusion of additional cohorts identified in 6-month data increments. Such sequential approach will extend initial analyses by allowing (1) examination of shifts in utilization patterns over time, and (2) inclusion of additional NOACs as they become available.

1 A complete list of all abbreviations used in the protocol is provided in [Appendix 4](#)

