3.1 DATA SOURCES

The data source for this project is a combination of claims data from UnitedHealth, a commercial health insurer, and MarketScan, a research claims database from commercial employer-sponsored health plans both of which provide comprehensive medical coverage for members with active policies.

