3.4 OUTCOMES

Patterns of anticoagulant medication use will be identified on the basis of a pharmacy dispensing. Pharmacy dispensing is considered the most accurate utilization measure short of electronic pillcounting caps. [\[R13-0543\]](#)

The primary outcomes considered include the proportion of patients dispensed specific anticoagulants and anticoagulant doses (for NOAC), as well as a description of the characteristics of these patients.

In addition, a variety of measures will be derived from features of the dispensing data, including: number of dispensings, characteristics of dispensings (dose, and days supplied), along with persistence measures (e.g., proportion with a single dispensing, proportion remaining on therapy over time, time until treatment switch or discontinuation). [\[R13-0542; R12-3689; P06-11504\]](#)
Treatment persistence over time constitutes the secondary outcome,

Table 3

[figure not shown]
Definition of utilization measures

Measure	Definition
Days supplied*	Number of days supplied by a dispensing
Dose**	Presumed dose based on # tablets, mg per tablet, and number of days
One dispensing only	Number (and fraction) of first anticoagulant recipients with no second dispensing
Persistence	Fraction of anticoagulant users with continued dispensings. Patients will be classified as persistent if they possess medication at the specified time point. Grace period of 14 days will be allowed to obtain an additional refill.
Anticoagulant switch	Dispensing of another anticoagulant within <30 days of the end of days supplied of the previous medication
Anticoagulant discontinuation	Treatment gap of ≥ 30 days (i.e., no dispensing of anticoagulant medication within 30 days of the end of days supplied)

*: Days supply likely reflects use patterns in a commercial insurer such as United Health or MarketScan.

**: Estimation of dose will be challenging during the dose titration period for warfarin. We explore warfarin dose over time and assess the feasibility of estimating average dose, seeking to identify maintenance dose (i.e., dose needed for consistent therapeutic INR).

***:

Notes:

Incident user: Patient with no dispensing of an oral anticoagulant in the prior 12 months

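### The yearly initiation rate is crude, so a change in the age, sex and stroke-risk mix of the source cohort can look like a change in initiation after NOAC launch

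*Combined protocol and SAP*

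**What the plan says.** **Aim.** Section 1 says of the sequential updates: "Such sequential approach will extend initial analyses by allowing (1) examination of shifts in utilization patterns over time". The same section names change in warfarin use after the NOACs arrive as something the study should help to understand.

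**Estimator.** Section 3.6.1, under the primary outcome on initiation over time: "The yearly anticoagulation initiation rate will be estimated as the proportion of patients who initiated treatment among the source cohort of patients". Members of that cohort must have atrial fibrillation without valvular disease, satisfy the criteria and not yet be treated. The denominator is built afresh for each calendar window. Anyone with at least one eligible day is found, a random index date is drawn, and "The cohort inclusion and exclusion criteria will be evaluated using this index date". Patients dispensed an anticoagulant before that date are removed unless they count as new initiators in that window.

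**Case mix.** For each new data block, section 3.6.1 says "we will characterize the patients newly initiated on treatment during that time period separately, in order to enable characterization of the shift in patient characteristics". Warfarin patients from before the October 2010 dabigatran launch are used to look for a shift in characteristics. Treatment groups are compared on characteristics only within a shared time window. Core Tables 2 and 3 (Appendix 1) give users' characteristics for all periods and for the latest one.

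**Adjustment.** The only adjustment visible is in the secondary persistence analysis: 1:1 propensity-score matching of each NOAC to warfarin within calendar quarter, followed by Kaplan-Meier. The summary table closing section 3.6.1 lists initiation as a yearly rate in the source population, with no adjustment or standardisation.

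**The concern.** A yearly proportion changes for two reasons: patients of a given age, sex and risk are treated differently, or the cohort contains a different mix of such patients. The crude rate adds the two together.

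The mix can move because each window's source cohort is redrawn. Plan membership turns over, and patients already treated leave the denominator, so the untreated pool in 2014 need not resemble that in 2009. If initiation differs by age or stroke risk, the crude rate moves even when prescribing within each stratum does not.

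This bears on a primary outcome and on a stated aim. Section 8 promises that the tables will be followed by an interpretive summary and a discussion of implications. That is where a movement in the crude rate could be put down to NOAC launch.

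**Working it through.** **1. The plan's own precision figures.** Section 3.2.1 uses s.e. = √(p(1−p)/n). At n = 10,000:
- p = 10%: √(0.10 × 0.90 / 10,000) = 0.30%, printed as 0.3%.
- p = 20%: √(0.20 × 0.80 / 10,000) = 0.40%, printed as 0.4%.

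All eight rows of Table 1 reproduce, including the 95% intervals (exact binomial). These are standard errors of one proportion. A trend needs the uncertainty of a difference.

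**2. Size of the artefact.** The documents give neither stratum-specific initiation rates nor a change in mix, so both are assumed: 20% initiation below 65, 35% at 65 or over, and no change in prescribing. With w the 65+ share, crude rate = 0.20(1 − w) + 0.35w.

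| 65+ share | Crude rate | Change from 50% share |
|---|---|---|
| 50% | 27.5% | – |
| 45% | 26.75% | −0.75 points |
| 40% | 26.0% | −1.5 points |
| 60% | 29.0% | +1.5 points |

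In general the change equals (change in share) × (difference in stratum rates). Standardised to the 50% mix, it is zero in every row.

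**3. Sampling noise.** For two years of equal size with rates near 27.5%, the 95% half-width of the difference is 1.96 × √(2 × 0.275 × 0.725 / n):
- n = 10,000: 1.24 points
- n = 15,000: 1.01 points

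A five-point mix shift (0.75) falls within this noise. A ten-point shift (1.5) exceeds it.

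**4. Which n applies.** The 10,000 to 15,000 a year in section 3.2.1 counts anticoagulant users, which is closer to the numerator. The size of the untreated denominator is not given. If the figure approximates yearly initiators, a 27.5% rate implies a denominator of 10,000 / 0.275 ≈ 36,000 to 15,000 / 0.275 ≈ 55,000. The half-width is then 0.65 to 0.53 points, and the five-point shift also exceeds it.

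**5. Other assumed rates**, starting from a 50% high-risk share:

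| Stratum rates | 2-point shift | 5-point shift | 10-point shift |
|---|---|---|---|
| 15% and 20% | 0.10 | 0.25 | 0.50 |
| 10% and 20% | 0.20 | 0.50 | 1.00 |
| 10% and 30% | 0.40 | 1.00 | 2.00 |

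The half-widths here are about 1.0 to 1.1 points at 10,000 a year and 0.8 to 0.9 at 15,000. At 10,000 only the 2.00-point case clearly exceeds noise; at 15,000 three of the nine cases do.

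**6. What the existing safeguards cover.** Matching within quarter and the common-window rule make drug-versus-drug contrasts fair at one time. Neither holds the mix constant from one year to another. The per-block description and the visible core tables on characteristics concern users. No visible core table describes the untreated source cohort by year, so a reader could not standardise the initiation rate afterwards.

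**The case against.** The strongest reply is that the study is descriptive. A crude proportion is a valid estimate of observed use, and no visible passage commits the authors to reading a trend as a change in prescribing at fixed case mix. Section 8 also says the tables will make no explicit comparisons. This stands as a reason to keep the crude rate. It does not cover the interpretive step, given the aim in section 1.

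A second reply is that the plan already reports shifting characteristics block by block. That would show a change among initiators, but it neither shows the mix of the untreated denominator nor removes its effect from the rate.

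A third is that text is missing. The synopsis sentence on how utilisation is examined breaks off, section 3.6.1 has a gap where it says how the characteristics analyses are conducted, the title of core Table 6 is blank, and section 3.2.1 mentions subgroups. Stratified trends cannot be ruled out, so the point is confined to what is visible.

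A reader might infer more than the documents support:
- **That the rate reflects whoever is insured.** It does not. The denominator is restricted to eligible, untreated patients with atrial fibrillation, and only the mix within that group matters.
- **That drug and dose shares should be standardised too, and trends drawn from that series.** Section 3.6.1 says "The analyses will describe the proportion of patients treated with various oral anticoagulants, as well as the characteristics of these patients". NOAC launch may itself change who starts treatment, so fixing the initiator mix could remove part of what section 3.2 wants described.
- **That the two databases will be misread against each other.** Sections 3 and 3.6 run every analysis separately by database, and no comparison between them is planned.

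**Conclusion.** The point holds for the primary initiation measure. It is an unadjusted yearly proportion in a cohort redrawn each window, and nothing visible keeps that cohort's age, sex and CHA2DS2-VASc mix constant, so a change in mix can be mistaken for a change in initiation.

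It would be wrong to conclude that the planned trend is false. The documents contain no evidence of a mix change and no stratum rates. The 0.75 to 1.5 points rest on assumed rates of 20% and 35% and assumed share shifts of 5 to 10 points. The comparison with noise rests on an assumed denominator. The artefact matters when the mix shift and the gap between stratum rates are both sizeable, or when the denominator is well above 15,000 a year. The weakness lies in interpretation, is inexpensive to remedy, and leaves the crude rate valid as a description of observed use.

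**What to change.** In core Table 1, keep the crude yearly initiation rate. Beside it, within each database, add a rate directly standardised to one fixed age-band × sex × CHA2DS2-VASc distribution of the source cohort, or show stratum-specific rates. Name the standard in advance so that it does not change as data blocks are added. State that the interpretive summary will consult both series before it describes a trend as a change in prescribing. Leave the drug and dose shares crude.

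No new data are needed: age, sex and the score are already required for eligibility and evaluated at the index date. The cost is one extra series per table and slightly wider intervals where cells are sparse. Broad bands will limit the latter; because the score itself counts age and sex, some combinations will be empty by construction. If the removed text already specifies age- or risk-stratified initiation rates, a cross-reference to them would suffice.
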